7.6.2 Serious Adverse Events and Adverse Event Leading to Discontinuation

Summaries of worst grade of on-study SAE, both by individual grade (1, 2, 3, 4, or 5, along with an Any Grade category) and by grade grouped as "Any, Grade 3-4 and Grade 5" will also be presented. This last summary will be repeated for:

- On-study drug-related SAEs
- On-study AEs leading to discontinuation.
- Drug related AEs leading to discontinuation

By-subject listings of SAEs and AEs leading to study drug discontinuation will be produced.

7.6.3 Adverse Events of Special Interest

Infusion reaction is a known elotuzumab toxicity. It will be based on investigator assessment and will be defined as any non-serious or serious adverse event judged by the investigator to be infusion related and which also occurs on the day of or the day after the elotuzumab infusion. These summaries will be presented:

- Frequency tables of the worst grade of on-study investigator infusion reaction (any grade and grade 1 through 5) by treatment group.
- Frequency of infusion reaction by infusion rate.
- Frequency of infusion reaction by cycle.

By subject listings of infusion reactions will be produced.

7.6.4 Second Primary Malignancies

By-subject listings of second primary malignancies (SPM) will be provided. Information on SPM will be obtained from the “Survival Status” eCRF page.

7.6.5 Deaths

The number and percentage of deaths and the investigator-reported cause of death will be presented, by treatment group and overall. This will be summarized for all deaths, and for those reported on study treatment or within 60 days of discontinuing study treatment.

7.6.6 Clinical Laboratory Evaluations

On-treatment laboratory tests for safety are defined as those that occur after first dose of any study therapy until 60 days after last dose of any study therapy.

The number and percentage of subjects with each worst severity grade for on-study hematology parameters (hemoglobin, Leukocytes, Lymphocytes (absolute), Absolute neutrophil count and platelet count) will be presented, by treatment group. Grades will be categorized as Grade 1, Grade 2, Grade 3, Grade 4, Any Grade and Grade 3-4. Subjects will be counted only once for each parameter, according to their worst post baseline CTC grade. The percentage of subjects with each worst severity grade will be calculated out of the number of subjects with a post-baseline (on-study) assessment for each lab parameter. Subjects with no on treatment assessment for a lab parameter will be reported in the “Not Reported” category.

This summary will be repeated for:

- Liver parameters (Alanine Aminotransferase, Albumin, Alkaline Phosphatase, Aspartate Aminotransferase, Total Bilirubin) with available CTC grades
- Renal/electrolyte parameters (sodium, potassium, bicarbonate, calcium, glucose, and creatinine) with available CTC grades. Sodium, potassium, chloride, calcium, and glucose will be presented separately, based on their high and low values.

For blood urea nitrogen (BUN), direct bilirubin, and total protein, the worst category on-treatment will be presented. Results will be categorized as; below upper normal limits, above upper normal limits or not reported.

For reporting purposes, urea will be converted to BUN, using the conversion factor: urea (mmol/L) / 0.357 = BUN (mg/dL).

Subjects experiencing any potential drug induced liver injury (DILI) will be summarized by treatment group as follows:

- A summary of the number and percentage of subjects with (AST or ALT > 3 × upper limit of normal (ULN)) and (Total bilirubin > 2 × ULN and ALP < 2 × ULN) will be presented.

If any potential cases of DILI are identified then clinical review will be conducted to ensure no other immediate apparent possible causes of AT elevation and hyperbilirubinemia are present, including but not limited to, viral hepatitis, pre-existing chronic or acute liver disease, or the administration of other drugs known to be hepatotoxic.

Note: The timing for total bilirubin rising to >2xULN needs to be concomitant with or within 30 days after ALT or AST rising to >3xULN. ALP needs to be <2xULN at the time of or within 2 weeks before ALT or AST rising to > 3xULN or TBILI>2xULN. This normal ALP value (<= 2xULN) must be present within 2 weeks of either the ALT/AST criteria or the TBILI criteria.

A by subject listing of all laboratory data will be provided. A separate listing will be provided for all subjects potentially experiencing DILI.

7.6.7 Echocardiogram, MUGA Scan and Electrocardiograms

A by subject listing of echocardiogram and multi gated acquisition (MUGA) scan data collected at screening will be presented. A separate by subject listing of electrocardiogram (ECG) data collected at screening will also be presented.

7.6.8 Vital Signs, Physical Measurements and Physical Examination

Vital signs parameters (body temperature, respiratory rate, seated diastolic and systolic blood pressure and heart rate) will be presented by visit and time point in a subject listing.

Physical measurements (weight and ECOG Performance Status) will be presented by visit and timepoint in a subject listing.

7.7 Pharmacokinetic Analysis

Elotuzumab concentrations taken pre (elotuzumab) dose, at each scheduled visit, will be summarized, by cycle and day, for subjects in the elotuzumab arm only. In addition to the standard summary statistics, the geometric mean will also be presented.

A by subject listing of elotuzumab concentrations will be provided.

Elotuzumab concentrations will be combined with concentration data from other studies and will be analyzed using population pharmacokinetic (PPK) analysis. Results of the PPK analysis may also be used to explore the relationship between elotuzumab and efficacy/safety endpoints. Results of the PPK analysis and potential exploratory exposure response analysis will be reported separately.

7.8 Anti-drug Antibody Analysis

ADA status of a sample:

- Baseline ADA positive sample: ADA is detected in the last sample prior to the first dosing date/time of elotuzumab.
- On study ADA positive sample: after the first dosing date/time of elotuzumab:
 - ADA is detected in a subject whose baseline is negative
- ADA is detected and ADA titer is at least 9-fold or greater (\geq) than the baseline positive ADA titers
- On study ADA negative sample: after the first dosing date/time of elotuzumab, no ADA detected relative to baseline.

Anti drug antibody (ADA) will be summarized for elotuzumab arm only with the following categories:

- Baseline ADA Positive Subject: A subject with Baseline ADA Positive Sample
- ADA Positive Subject: A subject with at least one ADA positive sample after the first elotuzumab dose relative to baseline.
 - **Persistent Positive**: ADA positive sample at 2 or more sequential timepoints at least 3 months apart
 - **Only the Last Sample Positive**: ADA positive sample only in the last sampling timepoint.
 - **Other Positive**: not persistent positive with ADA negative sample in the last sampling
 - **Neutralizing Positive**: At least one ADA Positive Sample with neutralizing antibodies detected.
- ADA Negative Subject: A subject with no ADA positive sample after the first elotuzumab dose relative to baseline.

A by subject listing of all ADA data at each time-point will be provided along with corresponding elotuzumab concentration values measured as a part of pharmacokinetic assessments.

The table content is completely redacted with black boxes. It appears to be a multi-column table with several rows of data.

8 CONVENTIONS

8.1 Baseline Definition

Baseline evaluations will be those performed within 60 days before randomization and prior to first dosing date. When an assessment is repeated multiple times within the screening evaluation period, the baseline evaluation will be the one closest to the first dosing date.

Laboratory tests and procedures (ECG, physical measurement and 2D echocardiogram MUGA, skeletal survey and plasmacytoma) done on the first date of dosing will be assumed to have occurred prior to dosing and therefore baseline evaluation for those parameters will be those prior or on the first dosing date.

8.2 Age Definition

Age (years) will be calculated as:

$$\frac{\text{date of informed consent} - \text{date of birth} + 1}{365.25}$$

8.3 Duration and Study Day Definition

In instances in which study period between two dates are to be calculated (for example, duration of response and PFS), the convention to be used is as follows: later date – earlier date + 1 day.

Study day is calculated as assessment date – first dose date + 1 day, if the assessment is taken on or after the first dose day. If the assessment is taken prior to the first dose day, study day will be calculated as assessment date – first dose date. Date of first dose is defined as Study Day 1.

8.4 Day Conversion of Date Imputation

Conversion from days to months or years:

- 1 year = 365.25 days
- 1 month = 30.4375 days

Imputation for partial or missing progression dates:

- If only the day is missing, the 1st of the month will be used to replace the missing day.
- If the day and month are missing or a date is completely missing, the date of progression will be moved back to the last complete tumor assessment date.

In both the cases given above, the imputed date will still be considered an event.

Imputation for partial or missing death dates:

- If only the day is missing, the later of the last known alive date and the 1st of the month will be used to replace the missing day.

- If both the day and the month are missing, the later of the last know alive date and Jan 1st will be used to replace the missing information.

In both the cases given above, the imputed date will still be considered an event.

For partial dates of start of subsequent anti-myeloma therapy, the following conventions will be used:

- When the day is missing, the alternative therapy will be assumed to start on the first day of the given month if this day is later than the last dosing date. Otherwise the alternative therapy will be assumed to start on the day following the last dosing date.
- When the day and the month are missing, the alternative therapy will be assumed to start on the first day of the given year if this day is later than the last dosing date. Otherwise the alternative therapy will be assumed to start on the day following the last dosing date.

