4.1.2.3 Primary Definition of Progression-Free Survival (PFS)

Primary Definition of PFS: PFS, under the primary definition, is the time from randomization to the date of the first documented tumor progression, as determined by the investigator using the IMWG criteria, or to death due to any cause, provided, progression or death does not occur more than 10 weeks (two or more assessment visits) after the last adequate tumor assessment. Clinical deterioration will not be considered progression.

The following censoring rules will be applied to the primary definition of PFS:

- Subjects who receive subsequent systemic secondary anti-myeloma therapy prior to documented progression will be censored at the date of the last adequate tumor assessment prior to or on the initiation of the new therapy.
- Subjects who have an event (documented progression or death) > 10 weeks (2 assessment visits) after their last tumor assessment will be censored at their last adequate tumor assessment prior to the event.
- Subjects who neither receive subsequent therapy prior to progression nor have a progression event will be censored at their last adequate tumor assessment.
- In addition, subjects who do not have any post-baseline tumor assessments and who do not die within 10 weeks of randomization will be censored on the date of randomization.

In all cases, if there are no adequate assessments for censoring then the subject is censored on the date of randomization

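### SAP 8.4 imputes incomplete progression dates with no lower bound and no stated order against the 10-week censoring rule

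*SAP*

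**What the plan says.** SAP 8.4 gives two rules for incomplete progression dates.

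- Rule 1, day missing: "If only the day is missing, the 1st of the month will be used to replace the missing day".
- Rule 2, day and month missing or no date at all: "the date of progression will be moved back to the last complete tumor assessment date".

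For both it adds: "In both the cases given above, the imputed date will still be considered an event". The word *complete* is not defined. The defined term, in SAP 4.1.2.1, is an *adequate* assessment, meaning one with enough information to rule out progression.

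The same section does bound its other imputed dates. For a death with the day missing, "the later of the last known alive date and the 1st of the month will be used to replace the missing day". For subsequent anti-myeloma therapy, the 1st of the month (or of the year) is used only if it is later than the last dose: "Otherwise the alternative therapy will be assumed to start on the day following the last dosing date".

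The primary PFS definition (SAP 4.1.2.3) counts an event only if "progression or death does not occur more than 10 weeks (two or more assessment visits) after the last adequate tumor assessment". A subject whose event comes more than 10 weeks "after their last tumor assessment will be censored at their last adequate tumor assessment prior to the event". The ITT definition (SAP 4.1.2.4) has no such condition. Duration of response (SAP 4.1.3) takes its end date from the primary PFS definition. Assessments are planned every 4 weeks (SAP 2.1).

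**The concern.** A progression date should fall after the last visit that showed the subject to be progression-free. SAP 8.4 does not ensure this. It can record progression on or before such a visit, or before randomization if the only complete assessment is the baseline one. The section guards against the equivalent contradiction for deaths and for new therapy, so the omission looks unintended.

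The second difficulty is order. The 10-week rule depends on the distance between the progression date and the last assessment, and imputation shortens that distance. SAP 8.4 says that imputed dates remain events, SAP 4.1.2.3 says that late events are censored, and no text ranks them. Two programmers following the SAP could classify the same subject differently in primary-definition PFS and in duration of response.

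**Working it through.** The plan states no figure that depends on these rules, so there is nothing of its own to reproduce. The checks below apply the rules as written.

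**Inputs.** Visits every 28 days (SAP 2.1); a 10-week limit of 70 days (SAP 4.1.2.3); Rules 1 and 2 (SAP 8.4). Assumption: the true progression date is equally likely to be any day of a 4-year calendar, which has 1,461 days and 48 months.

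**Rule 1 against the previous negative visit.** If that visit was *k* days before progression, the 1st of the month falls on it when the day of the month is *k* + 1, and before it when the day is later. For *k* = 28:

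- On the visit (29th of the month): 45/1,461 = 3.1%.
- Before the visit (30th or 31st): 44 + 28 = 72, and 72/1,461 = 4.9%.
- Together: 117/1,461 = 8.0%.

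For *k* = 21 the share is (1,461 − 21 × 48)/1,461 = 453/1,461 = 31%. For *k* = 35 it is 0%. Example: negative visit on 2 March, progression on 30 March, day not recorded; the imputed date is 1 March.

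The backward shift is the day of the month minus 1: mean 14.7 days, maximum 30.

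**Rule 1 against the 10-week rule, if that rule is applied after imputation.** A true gap of *g* days becomes *g* − (day of month − 1). It escapes censoring if the result is 70 or less.

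| True gap (days) | Share of dates with imputed gap ≤ 70 |
|---|---|
| 71 | 1,413/1,461 = 97% |
| 84 | 789/1,461 = 54% |
| 98 | 117/1,461 = 8% |
| 100 | 28/1,461 = 2% |
| 101 or more | 0% |

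**Rule 2.** If the last complete assessment is the last negative visit, the imputed gap is 0 days. Progression then always sits on a visit that ruled it out, and the 10-week limit can never be exceeded. The shift is 28 days if progression was found at the next scheduled visit, and the whole gap if visits were missed.

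**Effect on the Kaplan-Meier median.** This is a simulation of one arm of 40 with visits every 28 days, exponential PFS and administrative censoring spread over 24 to 40 months (1,500 replicates per row). The median PFS and the fraction of progression dates imputed are assumptions; neither is in the documents. Rule 1 shifts are drawn from 0 to 30 days; Rule 2 shifts are 28 days.

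| Assumed median PFS | Fraction imputed | Median earlier by, Rule 1 | Median earlier by, Rule 2 |
|---|---|---|---|
| 18 months | 2% | 0.3 days | 0.5 days |
| 18 months | 5% | 0.6 days | 1.5 days |
| 18 months | 10% | 1.4 days | 3.0 days |
| 24 months | 2% | 0.3 days | 0.5 days |
| 24 months | 5% | 0.9 days | 1.1 days |
| 24 months | 10% | 1.4 days | 2.5 days |

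The simulation has no missed visits, so it does not measure subjects moved from censored to event.

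**The case against.** Several points on the other side stand.

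- **The trigger should be rare.** Progression rests largely on dated samples, with serum and urine electrophoresis done centrally (Protocol 5.5), and investigators were told which component date to report (SAP 4.1.2.2). Against that, Protocol 3.6 lets data after treatment come from local providers, so some incomplete dates are plausible.
- **Early imputation may be a deliberate, conservative choice**, applied alike to both arms. That can justify an early date, but not one that contradicts a negative visit.
- **Little depends on it.** SAP 5 plans no formal comparison between arms, and the subject listing in SAP 7.5.2 would let odd records be seen.

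A reader might infer that Rule 2 always makes progression at least one 4-week interval early. The documents do not support a minimum. *Complete* could mean the last fully dated assessment, even the progression visit itself (shift 0), although the wording about moving the date back favors an earlier visit. Progression by imaging, marrow or calcium can also be found between scheduled visits.

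A reader might also infer that subjects due to be censored do become events. The sentence keeping imputed dates as events can be read as saying only that an incomplete date is not in itself a reason to censor, with the 10-week rule still to be applied. What the documents show is an unresolved order.

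**Conclusion.** The point holds as a minor defect in three parts: progression dates lack the floor given to death and subsequent-therapy dates, *complete* is undefined, and the order of SAP 8.4 and 4.1.2.3 is unstated.

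Under Rule 1 an imputed date contradicts the previous negative visit in about 8% of day-missing cases, given 28-day spacing and evenly spread dates. Under Rule 2 it does so every time, but only if *complete* means the last negative visit. The 10-week problem arises only if the limit is checked after imputation. Even then Rule 1 releases only gaps of 71 to 100 days, and visits kept on schedule never produce such a gap.

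The date shift enters both PFS definitions and duration of response. The 10-week question concerns primary-definition PFS and, through it, duration of response; it does not touch ITT PFS. ORR, the primary endpoint, is unaffected. A shift of about 0.3 to 3 days in the median, under the assumptions above, would not change how the trial is read, so an inference of material bias in PFS is not supported.

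**What to change.** Amend SAP 8.4 and 4.1.2.3 as follows.

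1. Day missing: use the later of the 1st of the month and the day after the last adequate assessment without progression, and never a date before randomization.
2. Month missing or no date: replace *complete* with the defined term *adequate*, and apply the same floor.
3. State that the 10-week rule is applied to the recorded visit sequence before any date is imputed.
4. Say whether a subject whose gap cannot be determined is an event or is censored. The floor alone cannot settle this, because with no date the true gap is unknown.

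With items 1 and 2, no imputed progression falls on or before a negative visit. The cost is a few lines of SAP text and the matching derivation code, with no new data.

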8.5 AE, Laboratory Results and Concomitant Medication

Safety data will be handled according to the BMS safety data conventions (described in “Analysis of Safety Data - Reference to CT SOP 109”). This document includes descriptions on how to analyze AE data as well as how to handle partial dates, missing dates, and unknown end dates when analyzing safety data.

The following dictionaries will be used to code medical terms and to derive toxicity grades:

- Adverse events and other symptoms will be graded according to the NCI CTC Version 3.0 and categorized according to the latest version of MedDRA at the time of the database lock.
- Laboratory results will be classified according to the CTC Version 3.0 grading system.
- All medications will be coded as per the latest version of the WHO Drug dictionary at the time of analysis.
- Tables and listings for laboratory results will be available in SI and US units.

[REDACTED]

[REDACTED]

[REDACTED]

[REDACTED]

[REDACTED]

[REDACTED]

[REDACTED]

[REDACTED]

[REDACTED]

APPENDIX 1 LIST OF ABBREVIATIONS

ADA	Anti-Drug Antibody
ADCC	antibody dependent cell-mediated cytotoxicity
AE	Adverse Event
ALP	alkaline phosphatase
ALT	alanine transaminase
AST	aspartate aminotransferase
ATC	Anatomical Therapeutic Chemical
BMS	Bristol Myers Squibb
CI(s)	Confidence Interval(s)
CR	Complete Response
CRF	Case Report Form

CSR	Clinical Study Report
CS1	CD-2 subset 1
CTCAE	Common Terminology Criteria for Adverse Events
DILI	drug induced liver injury
ECG	Electrocardiogram
ECOG	Eastern Cooperative Oncology Group
ESRD	End Stage Renal Disease
FISH	Fluorescence in situ hybridization
IHC	immunohistochemistry
IMiDs	induction, and bortezomib or immune modulatory drugs
IMWG	International Myeloma Working Group
ISS	International Staging System
ITT	Intent-to-Treat
IV	Intravenous
JNDA	Japan New Drug Application
KM	Kaplan-Meier
Ld	Lenalidomide, (low-dose) Dexamethasone
LdE	Lenalidomide, (low-dose) Dexamethasone, Elotuzumab
LDH	lactate dehydrogenase
MedDRA	Medical Dictionary for Regulatory Activities
MHLW	Ministry of Health, Labor and Welfare
MM	Multiple Myeloma
M-proteins	Monoclonal immunoglobulin
MUGA	Multi Gated Acquisition
NCI	National Cancer Institute
ORR	Objective Response Rate
OS	Overall Survival
PBMCs	peripheral blood mononuclear cells
